- **Form factor:** Mark I enclosure and integrated monitor, dedicated clinical monitor, keyboard and mouse on a single cart

- **Connections:** Clinical monitor for ECG and plethysmography (RS 232), 120 VAC power cord, sensor cabling to patient, remote connection via wifi for transfer of data (local USB connection also available)
- **Interface:** Monitor, On/Off switch, keyboard, mouse, Windows operating system for operation of subsystem software
- **Storage:** Adequate for 12 hours of all technologies (local storage)
- **Power:** 120 VAC, Battery back-up

We engaged System Insights, LLC in January 2021 to design and fabricate the hardware and controls for the Mark I prototype. System Insights is an engineering consulting company based in Norwich, VT specializing in custom electrical and mechanical systems. This prototype integrates EIS, EIT, NIRS, and ECG/Plethysmography subsystems for data collection and subsequent machine learning efforts. Subsystems and all components are housed in an enclosure to withstand the medical environment. The EIS subsystem consists of a Sciospec OEM system (ISX-3 mini) for receiving electrode signals and compiling data. The EIT subsystem consists of a Sentec Pioneer set for receiving electrode signals and processing data. The NIRS system is a custom device developed by Dartmouth College. ECG and Plethysmography data will be collected from an onsite GE clinical monitor.

Initial efforts by System Insights involved defining requirements for the system and working with the project team to integrate each subsystem. Initial design discussions resulted in some internal design specification documents for review to ensure the systems would meet the study demands. System construction of the first prototype occurred from March through July 2021. In addition to the sub-systems discussed previously, the system includes a medical-grade uninterrupted power supply to allow time for data collection to be safely stopped in the event of a power disruption and a central computer to operate subsystem-specific software packages. The central computer will also store data for wireless transmission to the offsite server or through a USB port. The system can be operated remotely or locally for ease of data transfer and remote troubleshooting. Of particular importance is that an operation manual has been developed for training purposes.

(Please note – a copy of the training and utilization manual
is included in Appendix II) I**

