In summary: we have developed a promising multi-technology poly-anatomic approach to development of noninvasive sensing in the setting of occult hemorrhage. The year one and year two studies used a rack system composed of commercial impedance and optical components. After evaluating the performance of individual components, we have been able to “prune” the court technologies to: impedance tomography, impedance spectroscopy, NIRS, plethysmography and ECG. The impedance and optical technologies have been incorporated into a first-generation prototype.

Phase III Trauma Validation and Re-Training Trial

Approach/Methods

Summary: We will enroll 480 trauma patients in a “no significant risk” prospective clinical trial to: 1) evaluate the performance of our Mark I prototype, 2) validate the performance of the Phase II algorithm and 3) re-train the algorithm to Phase III iteration.

This is not a therapeutic study. All technologies are non-invasive.

The main outcome variables are non-invasive measurements that will be used for machine learning, not real-time patient management. The data generated will be used later for discovery and validation in traditional and innovative machine learning.

Inclusion criteria:

1. Age ≥ 18
2. Patients suffering blunt and/or penetrating trauma
3. Awake and alert with GCS ≥ 14 as indicated by the treating provider/care team
4. Triage systolic blood pressure greater than 90 and heart rate less than 120

Exclusion criteria:

1. Need for ongoing fluid or pressor support (standard local fluid resuscitation only)
2. Signs of clinically significant ongoing external hemorrhage with active bleeding documented on radiology/ultrasound during initial evaluation (approximately 15 minutes post ED arrival)
3. Respiratory distress with O₂ saturation <96%
4. Pre-existing systemic illness, likely to alter systemic cardiovascular response to hemorrhage (overt clinical heart failure). Including congestive heart failure, and a paced cardiac rhythm.
5. Pregnant
6. Prisoner status
7. Anatomical abnormality or injury that would prevent placement of the electro-optical electrodes

Screening and Enrollment: The study team will approach ED patients initially evaluated by the Trauma team/ED care team in the Trauma room and currently being observed in a general ED bed who had met inclusion criteria. Those patients will participate in the informed consent process with study personnel following departmental and hospital SOP.

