 - 2nd set – is applied between the upper and lower SwissTom arrays adopting the same positioning technique as set one with respect to the mid-axillary line. In patients with the 2nd SwissTom array on the thigh, the 2nd ScioSpec EIS is also applied in this same truncal location.
 - 3rd set – applied on the right upper arm, “+” leads on the outside of the arm and “-“ leads on the inside, sandwiching the bicep.
- Please see device descriptions on pg. 12 for further detail

System Setup

CLINICAL MONITOR		
1. Clinical monitor: Open the desktop icon “iCollect - shortcut”	 iCollect - Shortcut	

2. At the following menu, ensure the settings in the orange box are as shown below and click “Online”

Patient Case Methods

- Research team member will turn on device and enter study identifier data.
- Research team member applies the device sensors as per Appendix II
- Research team member will confirm that data is being acquired.
- Device will remain attached to each patient until any of the following:
 - Stable for 6 hours (no signs of hemodynamic deterioration)
 - Disposition via discharge from the ED or admission to a care unit
 - Development of change from baseline hypotension or tachycardia below or above limits respectively.
 - The patient wishes for the device to be removed.
- The following data will be collected from the sensors: heart rate and electrical activity via electrocardiogram, transcutaneous oxygen saturation, blood pressure and arterial waveforms via finger plethysmography. Lastly, sensor data will collect changing perfusion physiology via electrical impedance tomography system.
- The study coordinator will extract relevant data from the patient's chart to complete a case enrollment form.
 - Data points from chart-
 - Gender

- Age (by decade)
- Height
- Weight
- Medications given during the ED visit and admission (if patient is admitted)
- Vital signs at triage and at “change in status.”
- Based on clinical chart review, the PI and co-PI will independently adjudicate each patient into either the “likely ongoing hemorrhage” or “likely no ongoing hemorrhage” outcome categories without reference to the algorithm results. In the event of differing results, the PI and the co-PI will meet and discuss until consensus is reached.
- At the quarterly milestones the existing data will be used iteratively to refine the Phase II algorithm, creating an initial Phase III algorithm.

Data Acquisition and Storage:

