SwissTom Impedance Tomography, NIRS Spectroscopy and ScioSpec Bioimpedance raw signals are all stored in a live, streaming fashion directly on an internal hard drive. All of this data is non-PHI and completely de-identified – only the subject number is incorporated into the file name. Similarly, any data collected by iCollect (mentioned above) has absolutely no PHI embedded within it and is live-captured and saved on an internal hard drive. At the end of the experiment all of this non-PHI, de-identified data will be uploaded to a secure cloud-based drive that has been approved by the participating institutions.

Data Analysis

At the completion of the study, the full data set will be used to define the performance of the Phase II algorithm with respect to the pre-specified performance criteria.

Data analysis will include the following steps:

- 1) **Data cleaning, filtering and validation:** All data will be processed to ensure that patterns are consistent with the underlying physiology. Any physiologically incorrect data will indicate issues related to loose electrodes, malfunctioning sensors,

etc. Such data will be filtered and cleaned to ensure that only meaningful data is used for algorithm testing.

- 2) **Data transformation and feature generation:** The cleaned, validated data will be transformed through a series of processing steps to generate the necessary features to be used in the supervised machine learning algorithms as predictors.
- 3) **Classification:** The features will then be used to generate machine learning-based predictions. These predictions will be compared against the ground reality of the patient's status to evaluate the algorithm performance.

Algorithm Performance Criteria: the algorithms developed will be trained to alarm under two circumstances indicating significant risk of ongoing hemorrhage progressing to shock: 1) a change from baseline, 2) development of prespecified patterns.

Performance will be judged on the basis of:

1. time of alarm before onset of deterioration
2. sensitivity, specificity, PPV, NPV for alarm/no alarm outcome
3. ROC curve and AUC for alarm/no alarm outcome
4. false-positive and false-negative rates

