- a. At the bottom left, confirm the software is showing the Sensor Belt Connector as Connected. If the software says the Sensor Belt Connector is disconnected, it indicates an internal power or connectivity problem, requiring the enclosure to be opened. Check if:
 - i. The power cable to the Pioneer Interface Module is fully inserted
 - ii. The cable connector on the front of the Pioneer Interface Module is connected

[figure not shown]
6. NIRS: Open the desktop icon, “NIRS - OceanView”

[figure not shown]
a. Upon initialization the Welcome Screen will look like this. Select Load a Saved Project.

[figure not shown]
b. Select the file, “Mark_1_Oceanview_Project_File.ocv” located at the following directory (if the correct folder does not appear initially): C:\Users\Baystate\Desktop\Software\Loaded to PCs\OceanView 2.0

[figure not shown]
c. Select the Flame-S spectrometer as shown below and click OK

d. Open “Configure graph saving” icon.

- e. **Uncheck** the option to stop after 1 sample.
- f. Configure the destination folder (Target Directory) to the desired Data Output directory and click **Apply**, then **Exit**

- g. **Sensor calibration:** The NIRS probes require some level of calibration data, by connecting the probes to the calibration blocks and collecting data as you would on a patient. This data is not needed regularly if the probes are consistently used on the same body part or do not get damaged. Label calibration data accordingly.

Data Collection

Prior to beginning data collection, quickly ensure all cables have been attached to the patient.

1. Clinical Monitor:

[figure not shown]
- a. Click the save (looks like a floppy disk) icon to start data recording.
- i. A window will pop up asking where to save the file. Navigate to the “Clinical Monitor” folder in the Data Output directory. Name the file “Patient number, date” and click OK. Data is now being recorded and saved.

- b. Click the stop icon to stop and save data at the end of measurements.

2. EIS:

- a. When ready to begin collecting data, click, “measure.” You should see measurements begin in the window below the setup heading.
- i. To view data as it is collected, right click the setup and select, “add new PlotterGrid – ABS/Phase”

[figure not shown]

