- ii. There are six plots: two plots per set of electrodes. One plot measures impedance (Z) vs frequency (f), and the other plots phase (Φ) vs frequency. Each plot is labelled at the top, indicating which group of EIS cables it corresponds to (see below table).

Slide Chip	Group Number	Probes Location
1 1 1 1	1	Arm
3 2 3 2	2	Chest
5 3 5 3	3	Leg

- iii. Impedance is measured in Ohms (Ω), phase is measured as an angle ($^{\circ}$), and frequency is measured in Hertz (Hz).
- iv. For the Z vs f plots, right click on the plot area and select, “double-log” view
 - 1. Impedance should be below 1,000 Ω . If the impedance is much higher, it likely means a poor connection at the electrode pad/patient interface
 - a. See the above table to help identify which group has the poor connection
 - b. After checking the electrode pad/patient connections (hair, peeling electrode pad, etc), the next place to check for connectivity problems if impedance is still high is the connection at the system enclosure. Remove and plug in the cable fittings of the problem group.

3. EIT:

[figure not shown]
- a. Click “Apply” to begin data measurements – the computer will not record/save the data until you select the save icon.

[figure not shown]
- i. Once you click “Apply” the other tabs should be selectable to see measurements and electrode connectivity
- ii. Check the “Sensor Quality” tab to check for any connectivity issues with the electrodes or cables

1. The best way to identify problem probes is by looking at the individual impedance values of each electrode
2. Electrode connectivity problems usually occur at the electrode pad/patient connection

- b. On the “Configuration” tab, click the green save icon to begin recording the data – the icon should turn red and the software will indicate data is recording

[figure not shown]

- c. The “Manage Files” icon will bring up a screen allowing you to view and access saved data, ensuring data is being recorded, and later, for copying completed files to the Data Output directory. The “Explore to Data Folder in OS” opens the folder containing the EIT data files.

[figure not shown]

4. **NIRS:**

- a. The probes should sequentially light up. If *not*:
 - i. If one light on the NIRS panel stays illuminated, it is indicating an error with the probe itself or a setting within the software
 1. Before replacing or repairing probes, try cycling the NIRS system power by turning off the Uninterrupted Power Supply
- b. Press the play icon

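### No step ties hospital-record time to Mark I time, so any clock offset enters lead time minute for minute when onset is timed from the chart

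*Combined protocol and SAP*

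**What the plan says.** Algorithm Performance Criteria lists four sets of measures. The first is "time of alarm before onset of deterioration"; the others are classification measures for alarm versus no alarm.

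**Alarm side.** Data Acquisition and Storage says that the impedance and NIRS "raw signals are all stored in a live, streaming fashion directly on an internal hard drive", and that the monitor data collected through iCollect "is live-captured and saved on an internal hard drive". The Mark I description gives the prototype "a central computer to operate subsystem-specific software packages". The algorithm is not run at the bedside: "The data generated will be used later for discovery and validation in traditional and innovative machine learning".

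**Onset side.** The definition of hemodynamic deterioration has five alternative criteria: sustained low systolic pressure with a raised heart rate, a relative rise in heart rate, a relative fall in mean arterial pressure, a clinician's decision that more fluid or blood products are needed, and a raised lactate. Under Patient Case Methods, "The study coordinator will extract relevant data from the patient's chart to complete a case enrollment form". The data points listed there include vital signs at triage and at the change in status, but no time of any event.

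**Set-up manual.** In Appendix II each recording is started separately. For the monitor the step is "Click the save (looks like a floppy disk) icon to start data recording"; for EIT it is "click the green save icon to begin recording the data". Folder and file names carry a date and a patient number. No step concerns a clock.

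**The concern.** Lead time is a difference between two times. If both are read from one clock, an error in that clock cancels. If the alarm is timed on the Mark I computer and the onset in the hospital record, the difference between the two clocks becomes part of the result. Staff who follow Appendix II exactly would leave no record of that difference.

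At stake is whether an alarm counts as early and by how much. A constant offset is a bias, and enrolling 480 patients does not reduce it. An offset that varies between patients widens the spread of lead times. Either can change the sign in a single case. Suppose, for illustration, that the chart clock runs 5 minutes ahead of the Mark I and the alarm comes 3 minutes after the true onset. The recorded lead time is −3 + 5 = +2 minutes, so a late alarm appears as an early one.

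**Working it through.** The plan gives no expected lead time, no clock tolerance and no figure for this measure, so there is nothing of its own to reproduce. The check has two parts.

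**1. Which clock can time each onset criterion?**

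| Criterion | Possible source of onset time |
|---|---|
| Lactate | Hospital record only; the Mark I has no such sensor |
| Clinician-defined need for more fluid or blood products | Hospital record only |
| Sustained low systolic pressure with raised heart rate; fall in mean arterial pressure | Unclear. Patient Case Methods lists blood pressure among the sensor data, but the Mark I list of sensing technologies omits it, and the Appendix II set-up attaches only ECG stickers and a finger probe to the dedicated monitor |
| Rise in heart rate | Mark I file through iCollect, or charted vital signs; the plan does not say which |

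At least two of the five criteria therefore depend on hospital-record time, and the two that involve blood pressure may do so as well. The plan names no source for onset time under any criterion. The set-up, data-collection, data-saving and shutdown steps of Appendix II contain no clock step. The cleaning step under Data Analysis deals with loose electrodes and faulty sensors, not with time.

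**2. How does an offset enter?**

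Recorded lead time = (true onset + chart clock error) − (true alarm + Mark I clock error) = true lead time + d, where d = chart clock error − Mark I clock error.

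If a share f of cases is chart-timed and d is constant, the bias in mean lead time is f × d. The documents give neither f nor d. With assumed values, in minutes:

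| f | d = 1 | d = 2 | d = 5 |
|---|---|---|---|
| 0.25 | 0.25 | 0.5 | 1.25 |
| 0.5 | 0.5 | 1.0 | 2.5 |
| 1.0 | 1.0 | 2.0 | 5.0 |

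The sign of the bias follows the sign of d.

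If d instead varies between patients independently of true lead time, the variances add. With an assumed true SD of 10 minutes and an offset SD of 5 minutes, the recorded SD in chart-timed cases is √(10² + 5²) = √125 = 11.2 minutes.

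**The case against.** The strongest reply is that one computer stores all the streams. If onset is read from heart rate in the iCollect file, and that file and the alarm signals carry the computer's time, the offset cancels. That stands, but only for such onsets and only on that condition. The monitor feeds the Mark I over a serial link, and the documents do not say whether its samples carry monitor or computer time. The iCollect settings screen is a figure that is not shown, and the case enrollment form is not in the documents. The absence of a clock step is therefore established only for the available text.

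Several stronger readings are tempting and are not supported:

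- **That every patient's lead time is shifted the same way.** This needs chart-timed onset in every case and a constant offset; neither is documented.
- **That starting the packages one after another misaligns the predictors.** Staggered starts do not misalign streams that carry timestamps, and the start instructions show no clock error.
- **That the retraining labels are shifted.** The labels described are one category per patient, adjudicated from the chart, with no time attached. An effect on the other listed performance measures is not shown either.
- **That the offset is lost for good.** Charted heart rate could be matched to the recorded trace for a rough estimate. With vital signs planned at only two charted points, that is not a reliable correction.
- **That the error is a given percentage of lead time.** The 20-25 minutes in the progress summary is a point in the pig model at which discrimination was assessed. It is not a lead time, and the plan states no expected lead time to divide by.

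It is also fair to say that lead time is listed first but not called primary, and that the sample-size statement refers to ROC-AUC. Finally, aligning clocks does not correct late charting or settle whether a lactate is timed at draw or at result. These points limit the concern and widen the remedy. They do not close the gap for the criteria that have no Mark I source.

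**Conclusion.** The point holds for chart-timed onsets. For at least the lactate and clinician-defined fluid criteria, lead time subtracts a Mark I time from a hospital-record time. No available step measures the offset between the two, and the chart data list does not ask for the time of the event. The offset then enters minute for minute, and a constant one biases mean lead time by f × d. The size cannot be found from the documents: 2.5 minutes follows from an assumed 5-minute offset with half the cases chart-timed, and across the assumed values above the bias runs from 0.25 to 5 minutes.

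The sources of both times are inferred, because the plan names neither. The inference is firm for the two criteria with no sensor and open for blood pressure and charted vital signs. Heart-rate onsets on a shared computer clock would be unaffected. The change should be made: lead time is a listed performance measure, the remedy is cheap, and the clock readings have to be taken at the bedside.

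**What to change.** 1. In the set-up and shutdown steps of Appendix II, set the Mark I computer and the dedicated monitor to the hospital's time source. Where that is not possible, write on the case form the times shown by the computer, the monitor and the chart system at the start and end of each recording.
2. Under Patient Case Methods, add to the chart data the recorded time of each onset event.
3. Under Algorithm Performance Criteria, name the timestamp source for each onset criterion. For lactate, say whether it is the draw or the result time. For blood pressure, say whether it is the device or the chart, and reconcile the sections that differ on whether the Mark I records it.
4. Under Data Analysis, state that all times are converted to one clock before lead time is computed.

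The cost is a short added step for research staff at each recording and a few case-form fields, with no change to patient care. Late charting would remain uncorrected and should be stated as a limitation.

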The dramatic advances in sensing technology and miniaturization have reached a stage at which it is now possible to: 1) put electromagnetic, optical and impedance technologies into small adhesive “dots” on the skin, 2) stream data from multiple anatomic locations, and 3) algorithmically transform these data such that the system alarms when it recognizes patterns suggestive of ongoing hemorrhage. We have been developing such a system, one that combines state-of-the-art noninvasive sensing technologies and advanced multivariable statistical algorithms. This system will be developed from its inception to be inexpensive and easily applied, even in austere settings.

Progress to Date: In years I and II the project made excellent progress in development of this technology. Using pre-existing data sets, we developed preliminary multivariate algorithms. We then developed a low-volume occult hemorrhage porcine model and utilized it for evaluation of a broad ensemble of noninvasive technologies and further development of the diagnostic/predictive algorithm.

We have successfully developed a sophisticated multivariate ML algorithm that provides superior performance at detecting/predicting bleed/no-bleed in occult hemorrhage and LBNP. The average ROC-AUC values are in the range of 97% 20-25 min. into our porcine low-volume occult hemorrhage model. This accuracy is far superior to all prior studies and better than our expectations at the start of the project with respect to what we anticipated being able to achieve at this stage of the project. We have successfully identified the principal drivers of this high accuracy: the largest contribution comes from the features generated from the raw impedance tomography signals, which in-and-of-themselves are able to provide an AUC value of higher than 80% on a consistent basis.

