Power and Sample Size: We anticipate acquiring data from every enrolled subject. Power and sample size calculations indicate that a sample size of 480 subjects should be sufficient to: 1) further identify the minimal subset of noninvasive measurement technologies necessary for the desired diagnostic performance, 2) validate the existing algorithms, and 3) initially train a human clinical iteration of the algorithms, with a sufficient degree of accuracy ($p < 0.05$ for ROC-AUC).

Enrolled patients will undergo standard electrocardiogram (3-lead) and oxygen saturation continuous monitoring.

In addition to these standard physiologic measurements, as a part of research, we will also acquire the following non-invasive optical and impedance measurements. All of these devices have been previously validated as non-invasive and safe in humans.

The clinicians providing care to the patient will be blind with respect to the measurements from these devices.

General Approach to Minimize Risk

This protocol will be minimal risk to patients as all these technologies have been robustly demonstrated to be safe (see below). There is minimal risk associated with placement of these devices and they can be removed at any time. They don't interfere with standard equipment used in clinical management of trauma patients. As described above, clinical management of the patient will not be affected by the study intervention.

Protection: Each subject will give informed consent after all questions have been answered by a study team member. Confidentiality of data will be assured by study specific coding of subject identities. No identified individual data will be presented or published; rather, group mean data will serve as the basis for comparisons. Procedures used in this study are performed regularly in the clinical setting by the investigators.

Any original signed paper consent documents, as well as any hard copy of study documents will be stored in a locked cabinet at Baystate Medical Center. Any electronic patient information will be stored on REDCap, a secure online database that is password-protected and only accessible by study personnel.

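### No alarm threshold is fixed before study outcomes are used, so sensitivity, specificity, predictive values and lead time can be read at a cut-off chosen on the evaluation patients

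*Combined protocol and SAP*

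**What the plan says.** Under Algorithm Performance Criteria (Data Analysis), the alarm is to be trained to fire in two circumstances: "1) a change from baseline, 2) development of prespecified patterns". Four bases of judgement follow:

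- Item 1: how long before deterioration the alarm fires.
- Item 2: "sensitivity, specificity, PPV, NPV for alarm/no alarm outcome".
- Item 3: "ROC curve and AUC for alarm/no alarm outcome".
- Item 4: false-positive and false-negative rates.

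The section does not state the size of change that triggers an alarm, the patterns, how the two triggers combine, the score behind the ROC curve, or the cut-off. The opening of Data Analysis calls the performance criteria pre-specified, but the list gives names of measures without values.

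Two other statements bear on the point. The last bullet of Patient Case Methods says that at each quarterly milestone the data in hand are used to refine the Phase II algorithm into an initial Phase III version. The first sentence of Data Analysis says that the full data set, at study completion, defines the performance of the Phase II algorithm.

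**The concern.** Every measure in items 1, 2 and 4 depends on where the alarm threshold sits. A lower threshold fires earlier and misses fewer patients, but gives more false alarms. If the threshold is set before the study's outcomes are seen, these measures are honest estimates. If it is set or adjusted on the same patients, they describe the best point on that sample's own curve and will not be reproduced in new patients. Items 1 and 2 could even be reported at different cut-offs.

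The plan creates this opportunity. The patients who contribute to the quarterly refinement are also in the final evaluation set, and nothing separates the two uses. Validating the Phase II algorithm is one of the three stated aims in the Approach/Methods summary, so an optimistic result would weaken a main product of the study.

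A smaller gap is that item 3 attaches the ROC to a two-level result without naming a score.

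**Working it through.** **Plan's own figure.** Under Power and Sample Size, 480 subjects are said to suffice, with p < 0.05 for ROC-AUC. This cannot be reproduced, because power, null AUC, alternative AUC, expected events and sidedness are not given. Only N = 480 is used below.

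**Assumptions, none of them in the documents.**
- One score per patient, normal with variance 1, with mean 0 in non-events and d′ in events.
- d′ = √2 · Φ⁻¹(AUC). For AUC 0.80, d′ = √2 × 0.8416 = 1.190.
- Event rates of 2, 5, 10 and 20%: 480 × 0.02 ≈ 10, 480 × 0.05 = 24, 480 × 0.10 = 48, 480 × 0.20 = 96 events.
- The cut-off t maximises sensitivity + specificity (Youden) in the same 480 patients.

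**Step 1: optimism from an in-sample cut-off.** In each of 4,000 simulated studies, t was chosen on the sample. Apparent sensitivity and specificity are the sample proportions at t. The true values at that t are sensitivity = 1 − Φ(t − d′) and specificity = Φ(t). Means over runs:

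| True AUC | Events | Apparent Se | True Se | Gap | Apparent Sp | True Sp |
|---|---|---|---|---|---|---|
| 0.80 | 10 | 0.814 | 0.672 | 0.142 | 0.742 | 0.740 |
| 0.80 | 24 | 0.783 | 0.696 | 0.087 | 0.734 | 0.731 |
| 0.80 | 48 | 0.763 | 0.707 | 0.056 | 0.731 | 0.726 |
| 0.80 | 96 | 0.749 | 0.713 | 0.036 | 0.732 | 0.725 |
| 0.97 | 10 | 0.961 | 0.856 | 0.105 | 0.921 | 0.920 |
| 0.97 | 24 | 0.940 | 0.883 | 0.057 | 0.917 | 0.915 |
| 0.97 | 48 | 0.930 | 0.894 | 0.036 | 0.914 | 0.912 |

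Almost all of the bias falls on sensitivity, because events are the scarce class. In patients, with AUC 0.80 and 24 events, apparent misses are 24 × (1 − 0.783) = 5.2. Expected misses at the same cut-off in 24 new events are 24 × (1 − 0.696) = 7.3.

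**Step 2: item 3 if the binary alarm is the ROC variable.** The curve joins (0, 0), (1 − Sp, Se) and (1, 1). Its area is ½(1 − Sp)Se + ½Sp(Se + 1) = (Se + Sp)/2. Under the same binormal model the largest value is Φ(d′/2):
- AUC 0.80: Φ(1.190/2) = 0.724.
- AUC 0.97: d′ = 2.660, so Φ(1.330) = 0.908.

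At specificity 0.95 the values are 0.637 (Se 0.325) and 0.897 (Se 0.845).

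**Step 3: the two effects are alternatives.** Step 2 needs an alarm fixed at one operating point, which leaves no cut-off to choose. Step 1 needs a score with a movable cut-off, in which case the AUC keeps its full value. One analysis cannot suffer both.

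**The case against.** The strongest defence is that the Phase II algorithm already exists, and that the quarterly work produces a different object, the Phase III version. On that reading the Phase II algorithm and any cut-off it carries stay untouched until the final evaluation. This may be what the investigators intend, but the documents do not say that the Phase II version or its threshold is kept unchanged. They speak of refining it, and the sentence on the two triggers says that the algorithms will be trained to alarm, which looks forward.

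A second defence is that outcomes are adjudicated without reference to the algorithm's results. That protects the outcome from the algorithm. It does not protect the threshold from the outcome.

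Three stronger readings are tempting but are not supported:

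- A reader might infer from item 3 that the AUC will collapse to a single operating point. Asking for a ROC curve presupposes a swept score, the classification step speaks of machine-learning predictions, and the team already reports AUCs for a bleed/no-bleed task. The item's label can simply name the classification being assessed. Two triggers are no bar either, since the maximum of two scores can be swept. What stands is an ambiguity.
- A reader might treat AUC as carrying the study's success rule. The p < 0.05 sits inside the sample-size statement with no null value and no rule for success.
- A reader might set the study's AUC against the porcine figure of about 97% under Progress to Date. No such comparison is planned, and the settings differ in any case.

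It is also fair that the study is non-therapeutic and that its measurements do not guide care in real time. That limits the harm to the validity of the performance claim.

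**Conclusion.** The concern holds for the threshold. As written, the plan lets the alarm cut-off be chosen on the patients used to evaluate it, and no freeze or hold-out prevents this. Under the stated model with true AUC 0.80, sensitivity would be overstated by about 0.14 with 10 events, 0.09 with 24 and 0.06 with 48. With true AUC 0.97 the gaps are about 0.11, 0.06 and 0.04. Specificity is barely affected. The direction does not depend on the binormal score, the Youden rule or the event counts, but the size does, and the documents give no event rate from which to narrow it. The simulation moves only the cut-off. Refitting the model itself on the same patients is not included.

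The ROC wording is a secondary matter. It needs clarifying, but it does not show that a binary AUC will be computed. The plan should be changed because the remedy removes a route to bias at almost no cost.

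**What to change.** 1. Patient Case Methods: before the first quarterly linkage of study outcomes to sensor data, freeze and archive the Phase II algorithm with its alarm threshold, including how the two triggers combine. State that quarterly refinement applies only to a separate Phase III copy.
2. Items 1, 2 and 4: report all of them at that one archived threshold, with confidence intervals.
3. Item 3: reword as the ROC curve and AUC of the frozen Phase II algorithm's continuous score, one score per patient.
4. Report any threshold re-optimised on study data only as part of Phase III training, and not as validation.

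The cost is a few lines of text and one archived file, with no extra patients or data. The real downside is that reported sensitivity may be lower, possibly materially, because the threshold would come from earlier data that are not from this trauma population (pre-existing data sets, the porcine model and LBNP). That loss would itself be a finding about how well the Phase II algorithm transfers.
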